the risk of unblinding. A member of the research team will program the headsets to either one of the two different relaxation programs and will explain to patient how to set up and use the device. The sham video group will watch a 2D conventional video projected in a virtual screen mimicking a void theater in the same headset, whereas the treatment group will have a full immersive experience with three-dimensional video and binaural audio. Other research team members and healthcare providers will be blinded to intervention assignment and pain assessment will be done by the blinded study coordinator. Patients will not use the video headset device during physical therapy or while ambulating and use of the headset will be restricted to the hospital.

Patients will be allowed to receive prophylactic anti-emetics during intraoperative time based on the risk assessment for nausea and vomiting. Postoperative anti-emetics for symptomatic treatment will also be allowed; ondansetron will be the first choice.

Patients will be followed-up by phone call one week after hospital discharge to ask them the Pain Outcomes Questionnaire Short Form (POQ-SF). No more than 3 attempts should be accomplished to contact the patients for the one-week post-discharge follow-up.

E. Measurements

Demographic and Background Information

Demographic data to be obtained includes height (cm), weight (kg), age (years), sex, ASA physical status classification, and self-declared ethnicity. Patients will be questioned for social history (tobacco) and medical history (pulmonary disease, kidney disease, diabetes mellitus, neurological disease, chronic pain conditions, illegal drug usage, alcohol abuse, myocardial infarction, previous surgery or stent placement and medications usage). Available preoperative laboratory tests and medication list will be recorded.

Standard anesthesia monitoring will be used. Data obtained from electronic medical records for intraoperative variables will include: duration of surgery, intraoperative opioid consumption and antiemetic medications.

Data for variables for the day of surgery as a baseline will be obtained from

Virtual Reality Distraction for Reduction in Acute Postoperative Pain

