electronic medical records for opioid consumption in PACU and ward; pain scores before surgery, in PACU and ward; requirement of oxygen in PACU and ward; nausea and vomiting, requirement of antiemetics, requirement of naloxone, and adverse events. Patient interaction with presented video content will be characterized using eye-tracking metrics.

Outcomes

All postoperative assessment will be made by an investigator who is strictly blinded to treatment allocation, and actual treatment (e.g., full immersion or sham distraction).

Primary Outcome

1. **Pain Scores.** We will assess pain using NRS scores (0-10, with 10 being worst) immediately before and 15 minutes after each intervention with the device, starting on postoperative day one (POD1) and until end of postoperative day two (POD2) or hospital discharge, whichever occurs first.

Secondary Outcomes

1. **Total opioid consumption.** We will measure total opioid consumption, converted to morphine milligram equivalents (MME), starting at the first pre-intervention pain score measurement, postoperative day one (POD1), and until the end of postoperative day 2 (POD2) or hospital discharge, whichever occurs first.
2. **Pain scores.** We will capture all pain score measurements done every 4 hours by standard of care starting at the first pre-intervention pain score measurement, POD1, and end of postoperative day two or hospital discharge, whichever occurs first, using NRS scores (0-10, with 10 being worst). Only the pain scores from routine nurse assessments will be used here (pain scores measured as a part of the primary outcome won't be included).
3. **Perception of video system usability.** Patient's perception of video system

Virtual Reality Distraction for Reduction in Acute Postoperative Pain

usability will be assessed using a validated questionnaire (System Usability Scale¹³) once after the last intervention with the device and before hospital discharge. The System Usability Scale is scored from 0 to 100 and higher scores are related with devices that are easier to use.

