4. **Post discharge pain outcomes.** Patients will be called one week after hospital discharge to assess post discharge pain outcomes using a validated questionnaire (Pain Outcomes Questionnaire Short Form¹⁴) which evaluates five domains (pain, mobility, activities of daily living, vitality, negative affect and fear). The Pain Outcomes Questionnaire Short Form is scored from 0 to 190 and higher scores are related with worst pain outcomes.

Tertiary Outcomes

1. **Anti-emetic medications.** We will record use of anti-emetic medications, and the outcome variable will be calculated as the number of anti-emetic medications administered starting at the first pre-intervention pain score measurement, POD1, until end of postoperative day two or hospital discharge, whichever occurs first.
2. **Patient mobility score.** We will measure patient mobility using physical therapy daily postoperative assessment (“6 Clicks” Basic Mobility Inpatient Short Form questionnaire¹⁵) starting at the first pre-intervention pain score measurement, POD1, until end of postoperative two or hospital discharge, whichever occurs first. The “6 Clicks” Basic Mobility Inpatient Short Form questionnaire is scored from 6 to 24 and higher scores are related with lower levels of functional impairment.

F. Data Analysis

We will assess the balance between randomized groups on baseline variables using the standardized difference (i.e., difference in means or proportions divided by the pooled standard deviation). For all analyses we will adjust for baseline variables having absolute standardized difference <0.10 ¹⁶. The analyses will be carried out using a modified Intention-to-Treat approach. More specifically, all patients who receive the treatment for

Virtual Reality Distraction for Reduction in Acute Postoperative Pain

any duration of time will be included in the analysis. For example, if a patient chose to withdraw on POD 2, their measurements from POD1 would still be used in the analysis. We'll only exclude patients who didn't receive any treatment at all either due to refusal or because they chose to withdraw.

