Primary outcome. We will assess the effect of VR on NRS pain score after each study treatment over postoperative days one and two using a linear mixed effects model on the series of post-VR pain scores while adjusting for the corresponding pre-VR pain score, with time and randomized group as fixed effect categorical variables. We will adjust for within-subject correlation across the pain scores using either an autoregressive AR (1) or unstructured correlation matrix, whichever has better fit (lower AIC, BIC). We will assess the group-by-time interaction, but even if significant ($P < 0.15$) the primary result will be made collapsing over time.

Secondary Outcomes

1. **Total opioid consumption.** We will assess the effect of VR on log-transformed total opioid consumption starting at the first pre-intervention pain score measurement, POD1, and until end of postoperative day 2 or hospital discharge, whichever occurs first, using a linear regression model.
2. **Pain scores.** We will assess the effect of VR on pain score over time starting at the first pre-intervention pain score measurement, POD1, and until end of postoperative day 2 or hospital discharge, whichever occurs first, using a linear mixed effects regression to account for within-subject correlation. Only the pain scores from routine nurse assessments will be used here (pain scores from Aim 1 won't be used).
3. **Perception of video system usability.** We will assess the effect of VR on perception of video system usability as measured by the System Usability Scale using a Wilcoxon rank-sum test and report the median difference (along with the 95% CI) estimated using the Hodges-Lehmann approach.
4. **Post discharge analgesia.** We will assess the effect of VR on analgesia scores one week after discharge using a Wilcoxon rank-sum test and report the median

Virtual Reality Distraction for Reduction in Acute Postoperative Pain

difference (along with the 95% CI) estimated using the Hodges-Lehmann approach.

Tertiary Outcomes

5. **Anti-emetic medications.** We will assess the effects of VR on the number of times a patient required anti-emetic medication within starting at the first pre-intervention pain score measurement, POD1, and until postoperative day 2 or hospital discharge, whichever occurs first, using a Wilcoxon rank-sum test, and report the median difference (along with the 95% CI) estimated using the Hodges-Lehmann approach.

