6. **Patient mobility score.** We will assess the effect of VR on patient mobility scores(s) during the postoperative day one (POD1), and until end of postoperative day 2 or hospital discharge, whichever occurs first, using a Wilcoxon rank-sum test, and report the median difference (along with the 95% CI) estimated using the Hodges-Lehmann approach.

Interim analyses. We will use a group sequential design to conduct interim analyses at each 25% of the planned enrollment to assess efficacy and futility of the intervention using a gamma spending function. Specifically, we will maintain the overall alpha level (monitoring efficacy) at 0.05 using gamma parameter of -4 [similar to O'Brien Fleming], and power at 90% (monitoring beta, type II error) using gamma parameter of -1 [more aggressive]. Under the alternative hypothesis (assuming a true difference of 1 point) the cumulative probability of crossing an efficacy (and futility in parentheses) boundary at the 1st through 4th analyses will be 0.08 (0.017), 0.36 (0.038), 0.71 (0.065) and 0.90 (0.10).

Sample Size Considerations. We base the sample size to have 90% power at the 0.05 significance level to detect a difference of 1 point or more between VR and placebo on the serial post-intervention NRS measurements in our linear mixed effects model. If we

Virtual Reality Distraction for Reduction in Acute Postoperative Pain

assume a SD of 1.5 points (taking into account the within-subject correlation in the repeated measures design), a total of 98 patients (49 per group) would be needed, and after adjusting for interim analyses, a total of 113. This sample size will also be sufficient for detecting moderate effect sizes in most of the other outcome variables.

Interim Pilot Study to Re-Assess variability.

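### The covariate rule is the wrong way round: it adjusts for baseline variables that are balanced and leaves out those that are not

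*Combined protocol and SAP*

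**What the plan says.** The opening paragraph of section 3.F sets out the purpose: "We will assess the balance between randomized groups on baseline variables using the standardized difference". The next sentence gives the operative rule: "For all analyses we will adjust for baseline variables having absolute standardized difference <0.10".

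Three analyses in 3.F can carry covariates:

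- The primary mixed model on post-session pain, fitted "while adjusting for the corresponding pre-VR pain score". That score is in the model whatever the rule says.
- The opioid analysis: "We will assess the effect of VR on log-transformed total opioid consumption", by linear regression, with no covariate named.
- The nurse-recorded pain scores, analysed "using a linear mixed effects regression to account for within-subject correlation", again with no covariate named.

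The other four outcomes (usability, post-discharge score, anti-emetics, mobility) use Wilcoxon rank-sum tests, which have no covariate term. The interim plan has four looks and aims to "maintain the overall alpha level (monitoring efficacy) at 0.05 using gamma parameter of -4".

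**The concern.** A standardized difference near zero means the groups are alike on that variable. Read literally, the rule adds a variable at 0.05 to the model and leaves out one at 0.3 or 0.4, the opposite of what a balance-triggered rule is for. Randomization is unstratified (section 3.D), so dealing with chance imbalance falls to the analysis.

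Two things are at stake. An imbalance in a prognostic variable stays in the realized estimate. The reported standard error can also be too small. The unadjusted test is slightly conservative when a prognostic variable happens to be balanced and slightly anti-conservative when it is not, and the two average to 5%. Adjusting only in the balanced case removes the conservative part and keeps the anti-conservative part.

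An analyst must either follow the rule as written or depart from it, possibly after seeing data at one of the four looks.

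**Working it through.** **1. The plan's own figures.** Inputs from 3.F, Sample Size Considerations: difference 1, SD 1.5, alpha 0.05 (two-sided, as in the re-estimation formula), power 90%. The normal formula gives 2 × [1.5 × (1.960 + 1.282)]² = 47.3, so 48 per group. The t-based version needs 49 (power 0.904, against 0.898 at 48), a total of 98 as stated. Numerical integration of the gamma spending design (four equal looks, non-binding futility) gives an inflation of 1.143, and 98 × 1.143 = 112, against the stated 113. These sample sizes are not in dispute. They put the looks at about N = 28, 56, 85 and 113.

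**2. How many variables the rule omits.** For an independent continuous baseline variable under 1:1 allocation, the chance SD of the standardized difference d is about 2/√N, so P(|d| < 0.10) = 2Φ(0.10·√N/2) − 1.

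- N = 28: 2Φ(0.265) − 1 = 0.21 adjusted, 0.79 omitted.
- N = 98: 2Φ(0.495) − 1 = 0.38 adjusted, 0.62 omitted.
- N = 113: 2Φ(0.532) − 1 = 0.40 adjusted, 0.60 omitted. The omitted variables have a mean |d| of about 0.22.

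**3. Uncorrected imbalance in a realized trial.** For one covariate with outcome correlation r, the unadjusted estimate shifts by about r × SD × d. At 49 per group, the mean of d given d ≥ 0.20 is 0.306. With r = 0.3 the shift is 0.3 × 1.5 × 0.306 = 0.14, and with r = 0.5 it is 0.23. A true effect of −1 then averages −0.86 or −0.77. Simulation gave the same values, and −0.99 to −1.00 with the inequality reversed.

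**4. Type I error, one covariate, single look, N = 113.** In large samples the unadjusted statistic is Z = rW + √(1−r²)·E, with W and E independent standard normals and W = d/(2/√N). For r = 0.5, the unadjusted test rejects 2.6% of the time when |d| < 0.10 and 6.6% otherwise. The rule adjusts in the first case, which raises that 2.6% to 5%: 0.405 × 5% + 0.595 × 6.65% = 6.0%. The same calculation gives 5.4% at r = 0.3 and 6.7% at r = 0.7. Simulation gave 6.2%, 5.3% and 6.6%.

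**5. Type I error, five covariates, primary-type model.** Simulation under no effect: 20,000 runs, Monte Carlo SE 0.15 to 0.2 percentage points, blocked 1:1 allocation, pre-score always in the model (assumed correlation 0.6). Covariates are reselected at each look. Efficacy boundaries are z = 3.155, 2.818, 2.439 and 2.014, and futility is not applied. R² is the assumed share of the variance remaining after the pre-score.

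| R² | Rule as written: single look / overall | Reported SE below true SD | Overall, inequality reversed | Overall, fixed list |
|---|---|---|---|---|
| 0.1 | 5.4% / 5.5% | 2% | 4.9% | 5.2% |
| 0.3 | 6.7% / 6.8% | 7% | 3.6% | 5.0% |
| 0.5 | 7.2% / 7.5% | 10% | 2.6% | 4.8% |

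Independent repeats put the overall figures for the rule as written at 5.5–5.7%, 6.7–7.2% and 7.5–8.0%. The mean estimate was within 0.003 SD of zero throughout. Compared with no covariates beyond the pre-score, the true SD of the estimate falls by at most 1% under the rule, and by 2%, 15% and 27% with the fixed list.

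**The case against.** The strongest reply is that this is a one-character slip with little numerical effect. The preceding sentence makes the intent plain, and the rule cites a paper on balance diagnostics. The primary model already adjusts each post-session score for its own pre-session score, so little prognostic variance may remain. The weak case (about 5.5%) is then at least as plausible as the strong ones, and nothing in the documents supports R² of 0.3 to 0.5. Planned power takes no credit for further covariates, so the fixed list's precision gain is not power the plan loses. Reversing the sign would remove the uncorrected imbalance, and being conservative does not breach 5%.

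Most of this stands as a limit on size. The sign is probably a slip, the effect may be small, and the one-covariate figures are only illustrative for the primary analysis. It does not remove the fault. This is the only statement of the rule, it reaches the primary analysis, and following it gives standard errors that are too small when covariates matter. The opioid and nurse-recorded pain models name no covariate of their own and are more exposed. A reversed rule would still choose covariates from the data: with 20 candidate variables it would select about 16 at N = 28 (20 × 0.79) and 12 at N = 113 (20 × 0.60).

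**Conclusion.** The concern holds. The rule as written selects balanced variables and omits imbalanced ones in the three model-based analyses, and no other text corrects it. It must be fixed because it is a wrong operative rule in the primary analysis, not because the numerical effect is large.

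The estimate is unbiased across randomizations. Overall type I error is near nominal for weak covariates and roughly 7% to 8% for strong ones, with standard errors up to about 10% too small. These sizes rest on assumed covariate-outcome correlations, on one summary per patient in place of the full repeated-measures model, on reselection of covariates at each look, and on no futility stopping or sample size re-estimation. The direction of the error and the share of variables omitted do not depend on the assumed correlations.

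Separately, the four Wilcoxon tests cannot follow a rule said to cover every analysis. That is a wording point and adds nothing to the severity.

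**What to change.** Replace the rule with a short pre-specified list drawn from data already collected. Section 3.E provides the candidates: "Demographic data to be obtained includes height (cm), weight (kg), age (years), sex, ASA physical status classification, and self-declared ethnicity", and from the day of surgery "opioid consumption in PACU and ward; pain scores before surgery, in PACU and ward". One workable list is age, sex, hospital, day-of-surgery opioid consumption and day-of-surgery pain. All precede randomization, which section 3.D places on the morning of the first postoperative day.

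- Use the list in the primary, opioid and nurse-recorded pain models at every look, whatever the observed balance.
- Keep the pre-VR score in the primary model.
- Keep standardized differences as description, or for a sensitivity analysis that adds variables at 0.10 or above.
- Limit the adjustment sentence to the model-based analyses.

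If the sponsor wants only the minimal repair, reversing the inequality to ≥ 0.10 restores the evident intent, but the choice of covariates stays data-driven and the test becomes conservative.

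The cost is SAP wording and about five degrees of freedom in each of three models. The planned 98 and 113 do not change.

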Patients will be randomized to either sham video headset group or video headset analgesia group. Study coordinators will be assigned to either randomize and program headsets, or to assess patients' during sessions. All enrolled patients will receive education by research team who will demonstrate how to adjust the headset strap, activate the device, and adjust the volume following a predetermined script with the goal of making patients feel comfortable using the device on their own. Patients will be assured they will receive the routine pain control in addition to video headset experience.

Anesthetic management will follow pre-established clinical and institutional guidelines. Anesthesia will be at attending anesthesiologist's discretion; usually that will be spinal anesthesia without intrathecal opioids. Intraoperative and postoperative opioids will also be given at the discretion of the attending anesthesiologist. Prophylactic antibiotics will be given per surgical routine. Other intraoperative and postoperative medications may be used and include anti-inflammatory medications, gabapentin, pregabalin, ketamine, or lidocaine patches. Clinicians will be encouraged to give a single dose of dexamethasone (4-8 mg) for PONV prophylaxis. Inhaled steroids will be permitted as necessary to treat reactive airway disease.

Patients will be randomized in a 1:1 ratio to either relaxation program the morning of the first postoperative day, before start the intervention. Randomization will be based on computer-generated codes with random blocking and no stratification. Allocation will be concealed by a web-based system. The use of the video headset will be offered postoperatively while patients are awake between 8 AM to 4 PM. **Each session will have a maximum duration of 8 minutes. We will target 3 session per day, with at least one hour separating each treatments.** Treatments will continue for two postoperative days or until hospital discharge, whichever comes first.

The study device is a Pico G2 4K headset, but all labels will be masked to reduce

Virtual Reality Distraction for Reduction in Acute Postoperative Pain

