We plan to re-estimate the sample size at the first interim analysis. For the outcome, the variance (σ^2) and ICC (ρ) will be estimated from the enrolled patients. Further, the correlation coefficient (r) between pre-intervention and post-intervention pain scores was also estimated. The variance for the outcome (σ^2) will be estimated for each of the pain score measurements separately and the most conservative (i.e., highest variance) option will be selected. Correlation coefficient was calculated in a similar manner and the lowest one was selected. For estimating ICC (ρ) a linear mixed effects model will be set up. We'll obtain estimates of between subject variance (σ_b^2) and total variance (σ_t^2) from the model and estimated ICC as σ_b^2/σ_t^2 .

Such a re-assessment “nuisance” parameters, does not affect the statistical properties of the design (i.e, does not increase type I error or decrease power). Keeping everything else the same as initially planned (90% power at the 0.05 significance level to detect a difference (Δ) of 1 point or more, 4 total analyses), we will calculate the new sample size using the equation below^{17,18}, where n is the number of observations required per group and m is the average cluster size. The total variance will be estimated by calculated by estimating the total variance for each observation separately and selecting the most conservative (i.e., highest variance) option. Correlation coefficient will be calculated in a similar manner. The number of patients required per group (N) would then be n/m .

$$n = \frac{(Z_{1-\alpha/2} + Z_{1-\beta})^2 2\sigma^2}{\Delta^2} \times (1 - r^2) \times (1 + (m - 1)\rho)$$

Virtual Reality Distraction for Reduction in Acute Postoperative Pain

If an increase in the total sample size is deemed necessary, the primary analysis will be carried out using the efficacy/futility boundaries for the new sample size.

Virtual Reality Distraction for Reduction in Acute Postoperative Pain

Addendum.

A. Pain Outcomes Questionnaire Short Form¹⁴ (POQ-SF)

01. On a scale of 0 to 10, with 0 being no pain at all and 10 being the worst possible pain, how would you rate your pain on AVERAGE on the LAST WEEK?

← 0 1 2 3 4 5 6 7 8 9 10 →
No pain Worst possible pain

02. Does pain interfere with your ability to walk?

← 0 1 2 3 4 5 6 7 8 9 10 →
Not at all All the time

03. Does your pain interfere with your ability to carry/handle everyday objects such as a bag of groceries or books?

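### The primary model chooses only between AR(1) and unstructured correlation and names no patient random intercept; if a persistent patient effect remains, single-look type I error is about 5–8% under AIC and 5–11% under BIC

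*Combined protocol and SAP*

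**What the plan says.** Section 3.F, Primary outcome, specifies a linear mixed effects model for the post-session scores. It adjusts for the matching pre-session score, "with time and randomized group as fixed effect categorical variables". Within-subject correlation is handled "using either an autoregressive AR (1) or unstructured correlation matrix, whichever has better fit (lower AIC, BIC". The group-by-time interaction is examined, but "the primary result will be made collapsing over time". The section names no random effect, compound-symmetry option, robust standard error or degrees-of-freedom method.

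Section 3.D gives the number of repeated scores: "We will target 3 session per day, with at least one hour separating each treatments" and "Treatments will continue for two postoperative days or until hospital discharge, whichever comes first". That is at most six per patient, and fewer after early discharge. Section 3.B requires only one anticipated night in hospital.

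Under Interim analyses the sponsor will "conduct interim analyses at each 25% of the planned enrollment", and states that "we will maintain the overall alpha level (monitoring efficacy) at 0.05 using gamma parameter of -4". Under the heading on re-assessing variability, the plan adds: "For estimating ICC (ρ) a linear mixed effects model will be set up". That model yields a between-subject variance, but its result is used only to re-estimate sample size.

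**The concern.** Under AR(1), two scores five sessions apart are treated as almost unrelated unless the lag-one correlation is high. If some patients report consistently more or less pain than their pre-session score predicts, the correlation does not fade in that way. The variance of a patient's average is then understated, and so is the standard error of the group effect, because the primary result averages over sessions. The confidence interval is too narrow and the P value too small.

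The unstructured option would capture a persistent effect, but it costs many parameters, so an information criterion may keep AR(1) when AR(1) is wrong. AIC and BIC also penalise parameters differently, and the plan names both without saying which prevails. The primary P value can therefore depend on an unstated choice. The same rule would apply at all four looks, where the plan promises an overall alpha of 0.05.

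**Working it through.** **The plan's own figure.** With a difference of 1, SD 1.5, two-sided alpha 0.05 and 90% power, the normal formula gives 2 × (1.960 + 1.282)² × 1.5² / 1² = 47.3, so 48 per group. The t-based calculation needs 49 per group (power 0.904), hence the stated 98. The plan gives 113 after interim adjustment; non-binding futility gives an inflation of 1.130 and about 111. The documents state no error rate for the correlation rule.

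**Inputs.** From the documents: up to 3 × 2 = 6 sessions, 1:1 allocation, 113 patients, four looks, alpha-spending gamma −4. Assumed: no random intercept is fitted, and the residuals have exchangeable correlation ρ of 0.1–0.5 after pre-score adjustment.

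**Step 1: error if AR(1) is the structure used.** Fitted to exchangeable data, AR(1) settles at a lag-one value of about ρ. With m sessions its weights are 1 for the first and last session and 1 − ρ for the others. Let S = m − (m − 2)ρ be the sum of the weights and Q = 2 + (m − 2)(1 − ρ)² the sum of their squares. For a patient's weighted mean, in units of the residual variance:

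- variance the model reports: (1 + ρ)/S
- true variance: (1 − ρ)Q/S² + ρ
- type I error: 2 × P(Z > 1.96 × k), where k = √(reported/true)

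For m = 6 and ρ = 0.3: S = 4.8 and Q = 3.96. The reported variance is 1.3/4.8 = 0.2708. The true variance is 0.7 × 3.96/23.04 + 0.3 = 0.4203. So k = 0.803, 1.96k = 1.573, and the type I error is 11.6%.

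| Sessions | k over ρ 0.1–0.5 | Type I error given AR(1) |
|---|---|---|
| 6 | 0.793–0.886 | 8.3–12.0% |
| 4 | 0.884–0.943 | 6.5–8.3% |
| 3 | 0.939–0.973 | 5.7–6.6% |
| 2 | 1.000 | 5.0% |

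If the remaining residual also has serial correlation of 0.3–0.6, the ranges are 5.6–8.9%, 5.2–6.7% and 5.1–5.7% at 6, 4 and 3 sessions.

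**Step 2: how hard the rule leans to AR(1).** Unstructured has m(m + 1)/2 covariance parameters and AR(1) has 2. At six sessions that is 21 − 2 = 19 extra, a penalty of 38 by AIC and 19 × ln 113 = 89.8 by BIC. At three sessions it is 4 extra: 8 and 18.9.

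**Step 3: the written rule, single look.** This was simulated with 20,000 null trials per setting, 113 patients, REML, fixed effects for time, group and pre-score, and t on n − 2 df. BIC used ln(patients). Monte Carlo error is about 0.15–0.25 points. Entries are for ρ = 0.1/0.2/0.3/0.4/0.5.

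| Sessions | AIC, % | BIC, % | AIC and BIC disagree, % of trials |
|---|---|---|---|
| 6 | 8.0/7.4/6.1/6.3/6.5 | 8.3/10.1/10.9/10.0/7.7 | 11/65/93/66/20 |
| 4 | 6.1/6.2/5.9/5.6/5.3 | 6.4/7.1/7.6/7.5/6.5 | 15/47/75/70/41 |
| 3 | 5.4–6.0 | 5.4–6.4 | 16/33/50/60/54 |

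With half the patients at three sessions and half at six (4,000 trials), the rates are 6.2–7.9% (AIC) and 7.0–10.0% (BIC). With serial correlation of 0.3 added, six sessions give 6.4–7.3% and 6.4–9.3%; with 0.6 the range is 5.5–6.6%. Controls with two sessions, independence or a true AR(1) give 4.7–5.3%. A separate simulation of 4,000 trials per setting agreed: six sessions, ρ 0.05–0.7, AIC 5.4–8.3% and BIC 5.9–11.1%.

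**Step 4: four looks.** Looks at 28, 57, 85 and 113 patients used boundaries 3.158, 2.820, 2.441 and 2.015. The structure was re-selected at each look and futility was not applied. Overall type I error over ρ 0.1–0.5 is 7.5–8.9% (AIC) and 8.3–12.4% (BIC) at six sessions, 6.3–7.1% and 6.3–8.6% at four, and 5.6–6.1% and 5.5–6.6% at three.

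**Step 5: the alternative.** A random intercept with AR(1) residuals gives 4.5–5.6% at 113 patients in every setting with three or more sessions, 4.4–5.3% at 28 patients, and 4.6–5.5% overall across four looks. An uncorrected unstructured fit at 28 patients gives 11.3–12.0%, 8.1–8.8% and 6.7–7.6% at 6, 4 and 3 sessions.

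**The case against.** The strongest reply is that a linear mixed effects model normally carries a patient random effect, and that the plan uses the same term for the ICC model, which must have one. With a random intercept the inflation goes. That reading is possible. But the primary-outcome text spells out its within-subject adjustment as one of two correlation matrices, and the most direct implementation is exactly that, with no random effect. A confirmatory analysis should not turn on which reading the programmer takes.

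Other points stand as limits on size:

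- The residual correlation is not given. The pre-session score, taken immediately before each session, may absorb much of the patient effect. The planned ICC shows that a between-patient effect is expected, not that the primary model's residuals are exchangeable.
- The upper figures need all six sessions and BIC. Patients discharged early contribute fewer sessions.
- Part of the AIC excess has a different cause. At six sessions and ρ of 0.3–0.5 the AIC rate of 6.1–6.5% is essentially that of the unstructured fit without small-sample correction (6.0–6.5%). The plan names no degrees-of-freedom method, so that part rests on the t test assumed here.
- The four-look figures omit futility stopping; binding futility would lower them.
- A random intercept alone also held 4.4–5.7% in the separate simulation, so the AR(1) part of the remedy is not strictly required.

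None of this supplies the missing rule for when AIC and BIC disagree, or shows that AR(1) is safe when a persistent effect remains.

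**Conclusion.** The concern holds, conditionally. If no random intercept is fitted and a persistent patient effect survives pre-score adjustment, the rule does not hold 5%. Single-look error is about 5–8% with AIC and 5–11% with BIC, largest at six sessions and small at three. Across four looks without futility, the overall rate reaches 8.9% (AIC) or 12.4% (BIC) at six sessions. These are sensitivity figures, not a demonstrated failure of the trial, because the documents do not give the residual correlation or the sessions completed. What needs no such assumption is that the random-effects structure, the degrees of freedom and the choice between AIC and BIC are left open. The plan should be changed on this point; confidence in the size is medium.

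**What to change.** In section 3.F, Primary outcome, replace the AIC/BIC choice with one structure used at every look: a patient random intercept with AR(1) residuals, fitted by REML, with the group effect tested on between-patient degrees of freedom (patients minus 2 in the simulation). State the fallback: if the model does not converge, or if patients have at most two sessions, use the random intercept alone (compound symmetry). If an unstructured fit is kept, make it a sensitivity analysis with Kenward-Roger degrees of freedom.

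The cost is SAP wording and a few lines of code, with no new data. The downside is wider intervals than AR(1) alone would report. The simulated median standard error rose 13–25% at six sessions, 6–12% at four, 3–5% at three and 9–17% in the three/six mix (exchangeable correlation 0.1–0.5). It rose only about 1% where AR(1) was right. If a random intercept was always intended, there is no widening from adding it.
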